#### **14.4.2. Baseline Characteristics**

Demographic and baseline disease characteristics will be summarized. Data to be tabulated will include demographic features such as sex, age, race, and weight, as well as disease-specific characteristics, such as tumor stage and histology.

#### **14.4.3. Efficacy Analyses**

The primary analyses of efficacy will be based on the ITT Population. The interim analyses will be performed on the Evaluable Population.

The primary efficacy endpoint, ORR, will be based on the proportion of subjects with CR or PR using the central determination of disease response in Groups A and B, separately. The estimate will be accompanied by a two-sided exact binomial 95% CB.

Progression-free survival, OS, and DOR will be summarized descriptively for Groups A and B using the Kaplan-Meier method. For such subjects, the progression or censoring date will be determined based on described conventions ([Food and Drug Administration, 2007](#)).

Progression-free survival, median PFS, and the estimated rate at 6 months (PFS6) based on the Kaplan-Meier analyses will be reported separately for Groups A and B. For OS, the estimated rates at 3, 6, 9, and 12 months based on the Kaplan-Meier analyses will be reported for Groups A and B. For DOR, the estimate of the median based on the Kaplan-Meier analyses for Groups A and B will be reported.

Waterfall plots will be used to depict graphically the maximum decrease from baseline in the sum of the product diameters in measurable nodes and nodal masses.

Secondary analyses of efficacy will be conducted based on the ITT and Evaluable Populations using response as determined by both the central determination of disease response and investigator site. In these analyses, the primary efficacy endpoint, ORR, will be estimated using the proportion of subjects with CR or PR. The estimate will be accompanied by a two-sided exact binomial 95% lower CB.

##### **14.4.3.1. Interim Analyses**

Interim analyses of efficacy using the Evaluable Population will be performed after ORR has been determined in 25 evaluable subjects for both Groups A and B, separately. In both Groups A and B, the ORR using the local determination of disease response will be obtained. If the lower bound of a single-sided 95% confidence interval using the exact binomial method is less than 10% (i.e., 5 responses or less out of 25 patients) in either group, enrollment in that group will not continue. Below are the 95% single-sided lower confidence intervals for various response rates using a sample size of 25 patients and employing the exact binomial methodology.

Sample Size	ORR	Lower 95% Single-Sided Confidence Bound
25	7 (28%)	14.0%
25	6 (24%)	11.0%
25	5 (20%)	8.2% 
25	4 (16%)	5.7% 

Would result in stopping enrollment in that particular group(s).

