## **8.3. Dose and Schedule**

### **8.3.1. Dose and Mode of Administration**

Subjects will receive:

- CUDC-907 60 mg (2  $\times$  30 mg capsules) orally (PO) for 5 days on/2 days off (5/2) (21-day cycles)

CUDC-907 will be administered PO with meals ( $\pm$  30 minutes). CUDC-907 will be administered in the clinic on days of PK blood sampling, biopsy sampling, and on Day 1 of each cycle up to Cycle 13. Beginning on Cycle 14, in-clinic dosing will only be required on Day 1 of even numbered cycles (i.e., Cycles 14, 16, 18, etc.).

If a dose is missed or vomited, the subject will be instructed to skip that dose and report it to the Principal Investigator (PI) as soon as possible. Missed or vomited doses should not be made up.

Subjects must meet retreatment criteria in order to continue receiving study treatment (see [Section 10.5.2](#)).

Treatment delays and dose reductions will be allowed as specified in Section 10.5.3; however subjects who experience a Grade 4 DLT-like event must be discontinued from further study treatment.

For full study treatment details, see Section 10.

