### **10.5. Study Drug Administration**

#### **10.5.1. CUDC-907**

Subjects will receive CUDC-907 60 mg in 21-day cycles.

CUDC-907 will be administered orally at the assigned dose level and schedule, 60 mg on a 5/2 schedule.

All doses of study drug (in clinic and self-administered) will be administered with meals ( $\pm$  30 minutes) at approximately the same time each dosing day, if possible.

Dose and/or schedule intensity of CUDC-907 may be reduced per protocol due to toxicity.

In the absence of significant toxicity, each subject is expected to complete at least 1 cycle (21 days) of study treatment. However, subjects may continue to receive additional 21-day cycles of CUDC-907 treatment until disease progression has been documented or other discontinuation criteria have been met (Section 9.3.1).

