### 14.4. Statistical Analysis

The statistical analyses will be performed using SAS® version 9.4 or later (SAS Institute Inc., Cary, NC). A comprehensive statistical analysis plan (SAP) will be finalized prior to database lock.

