#### 14.4.1. Analysis Populations

The Intent-to-Treat (ITT) Population will consist of all subjects in Groups A and B. The primary analyses of efficacy will be conducted based on the ITT Population.

The Evaluable Population will consist of all subjects in Groups A and B who receive at least one full cycle of treatment and have at least one post-baseline disease assessment and have not had major protocol deviations that are thought to have materially impacted efficacy outcomes. Major protocol deviations will be identified prior to database lock. Secondary analysis of efficacy will also be conducted based on the Evaluable Population. In addition, the primary efficacy endpoint (ORR) will also be assessed using the Evaluable Population as a secondary analysis.

The Safety Population will consist of all subjects who receive any treatment. All safety analyses will be conducted based on this population.

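### Does the interim stopping rule need a wording change because the plan sets no date for fixing the 25 Evaluable subjects?

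*Combined protocol and SAP*

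**What the plan says.** Section 14.4.3.1 (and the synopsis) applies the interim rule to the Evaluable Population: "Interim analyses of efficacy using the Evaluable Population will be performed after ORR has been determined in 25 evaluable subjects", for Groups A and B separately, using the investigator's reading of response. If the one-sided 95% exact lower bound is below 10%, which the section translates as 5 or fewer responses in 25, then "enrollment in that group will not continue".

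Section 14.4.1 sets three conditions for being evaluable. Subjects must "receive at least one full cycle of treatment and have at least one post-baseline disease assessment", and they must "have not had major protocol deviations that are thought to have materially impacted efficacy outcomes". On timing it says only: "Major protocol deviations will be identified prior to database lock". Section 14.4 gives the analysis plan the same deadline: "A comprehensive statistical analysis plan (SAP) will be finalized prior to database lock".

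On the length of a cycle, section 10.5.1 says that, absent significant toxicity, "each subject is expected to complete at least 1 cycle (21 days) of study treatment"; the synopsis and section 6.2 also give 21 days. Section 8.3.1 adds: "Missed or vomited doses should not be made up". The primary analysis (sections 14.4.1 and 14.4.3) uses all Group A and B subjects and central response.

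**The concern.** The rule is worded as mandatory and its cut-off falls between two adjacent counts, so a single subject can settle it. Three features seem to leave that subject's status open.

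- The deviation criterion is a judgement, and its stated deadline, database lock, may come long after the interim.
- A full cycle could be read as 21 days elapsed or as the 15 doses that the 5-on/2-off schedule gives in three weeks (5 × 3). The text does not say how held or missed Cycle 1 doses count.
- The analysis plan that could settle both points is also due only by database lock.

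The study is open-label and the interim uses local response, so a subject could in principle be kept or dropped by someone who knows the result. At stake is a group closed when the rule should have let it continue, or kept open when the rule should have closed it.

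**Working it through.** **Inputs.** From section 14.4.3.1: n = 25 per group, one-sided 95% exact bound, threshold 10%. From section 14.3: planning ORR 30%. The true ORRs of 20% and 24% and the number of subjects with open status are assumptions; the protocol gives no rate of non-evaluable subjects.

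**1. The plan's own table.** The exact lower bound for x responses in n is the 5th percentile of a Beta(x, n − x + 1) distribution.

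| Responses in 25 | Computed bound | Plan |
|---|---|---|
| 7 | 13.95% | 14.0% |
| 6 | 11.01% | 11.0% |
| 5 | 8.23% | 8.2% |
| 4 | 5.66% | 5.7% |

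The table reproduces, and the cut-off lies between 5 (stop) and 6 (continue).

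**2. How often a group lands next to the cut-off.** P(X = 5) + P(X = 6), with X binomial(25, p):

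- p = 10%: 0.0646 + 0.0239 = 0.0885
- p = 20%: 0.1960 + 0.1633 = 0.3594 (from unrounded terms)
- p = 24%: 0.1749 + 0.1841 = 0.3589 (from unrounded terms)
- p = 30%: 0.1030 + 0.1472 = 0.2502

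These figures show how often the count is close. They are not the chance that an open status changes the decision.

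**3. How often one open status could matter.** Suppose one of the 25 has open status and, if excluded, is replaced by the next subject, since the rule waits for 25. Both decisions are reachable only if the other 24 hold exactly 5 responders and the open subject and the replacement differ in response. The probability is P(X = 5 | 24, p) × 2p(1 − p):

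- p = 10%: 0.0574 × 0.18 = 0.0103
- p = 20%: 0.1960 × 0.32 = 0.0627
- p = 24%: 0.1841 × 0.3648 = 0.0671
- p = 30%: 0.1177 × 0.42 = 0.0494

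This is the chance that both decisions are available. The decision actually changes less often, because the open subject must also be classed the wrong way.

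**4. More open subjects.** With three open at once, enumerating every possible choice of exclusions, both decisions are reachable in 3.1%, 18.8%, 20.1% and 14.8% of trials at 10%, 20%, 24% and 30%. This needs 3 of 25 (12%) to be unresolved at the interim and takes the most favourable selection in each direction. Nothing in the protocol supports such a number.

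**5. Is the status really open?**

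- *Timing.* The trigger is ORR determined in 25 evaluable subjects. Nobody can count to 25 without applying all three conditions of section 14.4.1, including the one on deviations. Database lock limits how late deviations may be identified; it does not prevent an earlier review, and the interim requires one.
- *Full cycle.* The protocol gives cycle length in days. The first scheduled on-treatment scan falls in days 15 to 21 of Cycle 2, ± 3 days (section 11.3.2). With no delay, the earliest date is study day 21 + 15 − 3 = 33. A response on a scheduled scan therefore comes after day 21, and on the 21-day reading this condition would not remove such a responder. Only a dose-count reading could, and no section uses one.
- *No replacement.* Dropping one non-responder from 5/25 without replacement gives 5/24, with a bound of 8.59%, which is still a stop. Five would have to go before the bound passes 10% (5/20, 10.41%).

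**The case for a change.** The strongest case for a change is that the rule is mandatory, is used in each of two groups, and turns on one responder, while the text nowhere requires a dated list of the 25 or a deviation review done without knowledge of response. Section 15.6 describes the Safety Review Committee as the Medical Monitor, the investigator and sponsor representatives, so no independent body is described that would supply the safeguard. A few sentences would cost no patients and no scans.

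Part of this stands. The protocol has no explicit freeze, and it does not say how held or missed doses count. But these are operational details. No stated rule gives a wrong answer, and the missing sentences would record what an analyst must already do to run the interim: list the evaluable subjects, note the exclusions and count responses.

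One could also ask for the ORR in all enrolled subjects of the group to be shown beside the Evaluable figure. That reopens the choice of denominator, which the plan discloses and applies consistently, and it would leave the rule, its cut-off and the primary result as they are.

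**Conclusion.** The concern does not call for a change. The trigger requires evaluable status to be judged when the rule is applied, and cycle length is given in days. What remains is a gap in detail that analysts fill sensibly.

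Its size is small. With one open and replaced subject, both decisions are reachable in 1.0% of trials per group at a true ORR of 10%, 6.3% at 20%, 6.7% at 24% and 4.9% at the planning value of 30%. The figures rest on an assumed single open subject and a replacement with the same response probability, and they are upper limits on changed decisions. The larger figures of 15 to 20% at ORRs of 20 to 30% need three unresolved subjects and worst-case selection.

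The consequence is confined to enrolment in one group. The sample size in section 14.3 is based on precision, with no hypothesis test, so no type I error is at stake. Interim evaluable status does not enter the primary ORR.

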#### 14.4.4. Safety Analysis

The analyses of safety will be conducted based on the Safety Population. Analyses will be stratified by treatment. Safety will be assessed based on AEs, SAEs, laboratory values, vital signs, and ECG results.

Summary tables will be produced for all reported treatment-emergent AEs (TEAEs), defined as AEs that start or worsen on or after the first administration of study treatment. The reported AE term will be assigned a standardized preferred term using the current version of the Medical Dictionary for Regulatory Activities (MedDRA).

TEAEs will be summarized based on the number and percentage of subjects experiencing the event by MedDRA system organ class and preferred term. The causal relationship between the occurrence of an AE and study treatment will be judged by the Investigator. In the event a subject experiences repeat episodes of the same AE, then the event with the highest severity grade and the event with the strongest causal relationship to study drug will be used for purposes of incidence tabulations.

Tabular summaries will be provided for:

- All TEAEs
- TEAEs by relationship to study treatment
- TEAEs by severity
- TEAEs occasioning treatment modification
- Serious TEAEs

All deaths that occur on study (defined as during treatment or within 30 days of treatment discontinuation) will be reported in a subject listing, which will include the primary cause of death and the number of days between the date of the last dose of study treatment and death. For subjects on combination treatment, the listing will show the date of last dose of each component.

Hematology and serum chemistries will be summarized using conventional summary statistics (mean, standard deviation, median, and range) for the following: baseline value, minimum and maximum post-baseline values, average post-baseline value, and last post-baseline value. Standard shift tables will also be prepared presenting worst post-baseline toxicity grade vs baseline. Vital signs and ECG results will be summarized in a descriptive manner by calculating

the mean, standard deviation, median, and range by time point in the same manner described for laboratory values.

Prior and concomitant medications will be coded to the generic term using the current version of the World Health Organization Drug Dictionary and will be tabulated by group and listed by subject.

#### **14.4.5. Pharmacokinetic Analysis**

Population PK analysis will be conducted to further understand the PK profile of CUDC-907 in patients with RR MYC-altered DLBCL. Linear mixed-effect modeling and/or a nonlinear mixed-effect modeling approach will be used in the study to better understand the PK profile of CUDC-907 in general. Preliminary PK information has been collected during Phase 1, and the basic PK models of the drug have been established. In this study, blood samples will be obtained at 2 hours post-dose on Cycle 1 Day 1, Cycle 4 Day 1, and on Day 1 of every other cycle thereafter (i.e., Day 1 of Cycles 6, 8, 10, etc.). In addition, for the first 50 subjects enrolled on amendment 4, blood samples will also be obtained 2 hours post-dose on Days 8 and 15 of Cycle 1.

#### **14.4.6. Multicenter Study**

Data will be pooled across centers for all analyses.

#### **14.4.7. Adjustments for Covariates**

No adjustments for covariates will be made.

#### **14.4.8. Missing Data**

Unless otherwise stated, there will be no imputation of missing data, but dates for AEs and concomitant medications may be imputed conservatively if partial.

## **15. STUDY ADMINISTRATION**

Regulatory authorities, the IRB/Independent Ethics Committee (IEC), and/or the Sponsor's clinical quality assurance group, or its designee, may request access to all source documents, eCRFs, and other study documentation for on-site audit or inspection. Direct access to these documents must be guaranteed by the Investigator, who must provide support at all times for these activities.

### **15.1. Case Report Forms and Source Documentation**

For each subject, an eCRF and corresponding source records will be maintained at each clinical site. The eCRFs should be completed in a timely manner, and every effort should be made to have electronic forms completed and up-to-date in anticipation of a visit by the Sponsor's monitor.

The Investigator must prepare and maintain adequate and accurate records of all observations and other data pertaining to the clinical study for each study participant.

All aspects of the study will be carefully monitored with respect to GCP and standard operating procedures for compliance with applicable government regulations. The study monitor will be an authorized individual designated by the Sponsor. The study monitor will have access to all records necessary to ensure integrity of the data and will periodically review the progress of the study with the PI.

An electronic data capture system to manage data collection will be utilized during this trial. The electronic data capture system is a software tool designed to ensure quality assurance and facilitate data capture during clinical trials. The system is fully compliant with Code of Federal Regulations 21 Part 11.

The Investigator will ensure the accuracy, completeness, and timeliness of the data reported to the Sponsor. Data collection processes and procedures will be reviewed and validated to ensure completeness, accuracy, reliability, and consistency.

A complete audit trail will be maintained of all data changes. The Investigator (or designee) will cooperate with the Sponsor (or its representative[s]) for the periodic review of study documents to ensure the accuracy and completeness of the data capture system at each scheduled monitoring visit.

### **15.2. Investigator Documentation**

Study staff will maintain appropriate medical and research records for this study, in compliance with International Conference on Harmonisation (ICH) E6, Section 4.9 and regulatory and institutional requirements for the protection of confidentiality of subjects. Study staff will permit authorized representatives of regulatory agencies to examine (and when required by applicable law, to copy) research records for the purposes of quality assurance reviews, audits, and evaluation of the study safety, progress and data validity.

The Investigator will provide the Sponsor with a fully executed FDA Form 1572 including the Investigator's curriculum vitae. The Investigator will indicate on Form 1572 the name and

location of the clinical laboratory which will be used for subject evaluation. The laboratory's certification, certification number, and date of certification and the laboratory normal values will be provided. Any changes in the clinical laboratory or laboratory values will be provided promptly to the Sponsor who will report the changes to the FDA as required.

### **15.3. Record Retention**

The Investigator will retain a copy of all study records in a secure location for a period of 2 years after the last approval of a marketing application and until there are no pending or contemplated marketing applications OR until at least 3 years have elapsed since the formal discontinuation of clinical development of the investigational product.

### **15.4. Protocol Deviations and Amendment**

The Investigator is not permitted to alter or deviate from the protocol without written agreement from the Sponsor. Any such agreement should be reported by the Investigator to their IRB/IEC. An immediate and unapproved deviation is permitted if immediate health care concerns mandate it.

All protocol revisions (amendments) must originate with and be documented by the Sponsor. The Investigator must submit the amendment to his/her IRB/IEC for review and approval prior to implementation. Documentation of approval signed by the chairperson or designee must be sent to the Sponsor.

### **15.5. Institutional Review Board/Independent Ethics Committee**

The protocol, ICF(s), recruitment materials, and all patient materials will be submitted to the IRB/IEC for review and approval. Approval of both the protocol and the consent form must be obtained before any patient is enrolled at any given investigative center, and a copy of the approval letter supplied to the Sponsor or Sponsor's designee. Any amendment to the protocol will require review and approval by the IRB/IEC before the changes are implemented in the study.

During the course of the study, the Investigator shall make timely and accurate reports to the IRB/IEC on study progress at intervals not exceeding one year, as well as satisfying any other local IRB/IEC reporting regulations. Copies of all reports to, and correspondence with, the IRB/IEC must be provided to the Sponsor or Sponsor's designee. Further, within three months of the completion or early termination of the study, a final report should be made to the IRB/IEC and Sponsor by the Investigator.

It is the Investigator's obligation to maintain an IRB/IEC correspondence file and to make this available for review to Sponsor representatives as part of the routine study monitoring process.

### **15.6. Study Committees**

A Safety Review Committee (SRC) comprised of the Medical Monitor, PI, and Sponsor representatives will be convened to review safety information for ongoing safety surveillance.

The SRC is tasked with making a recommendation to continue or stop the trial based on their assessment of available efficacy and safety information (see Section [9.3.2](#) for SRC stopping criteria).

### **15.7. Sponsor Monitoring**

Monitoring and auditing procedures approved by the Sponsor will be followed in order to comply with GCP guidelines. After satisfactory receipt of all necessary regulatory paperwork, the Sponsor's monitor will arrange that all study material be delivered to the study site at a mutually convenient time. An initiation visit by the Sponsor and its monitoring personnel will be made. At this meeting, all personnel expected to be involved in the conduct of the study will undergo an orientation to include review of study protocol, instruction for eCRF completion and overall responsibilities, including those for drug accountability and study file maintenance.

Throughout the course of the study, the Sponsor's monitor will make frequent contact with the Investigator. This will include telephone and/or on-site visits. On-site checking of the eCRFs for completeness and clarity, cross-checking with source documents, and clarification of administrative matters will be performed. As part of the data audit, it is expected that source documents (e.g., hospital records, office records) will be made available for review by the monitor. The monitor also will perform drug accountability checks, and may periodically request review of the Investigator's study file to assure completeness of documentation in all respects of study conduct.

Upon study completion, the monitor will arrange for a final review of the study files, after which the file should be secured by storage for the appropriate period as specified in Section [15.3](#). The Investigator or appointed delegate will receive the Sponsor's representative during these on-site visits and will cooperate in providing the documents for inspection and responding to inquiries that may arise as part of this review. The Investigator will also permit inspection of the study files by authorized representatives of the FDA and regulatory authorities of other countries.

